For the blood donor testing, if results of the investigational assay do not agree with the final specimen status based on supplemental testing, the donor may be asked to provide a follow-up sample. For these individuals providing follow-up samples, their consent to participate must be documented on an IRB-approved consent form prior to the collection of the follow-up specimen.

The specimens provided by Abbott were either obtained prospectively and are considered linked or are not individually identifiable. The specimens will be identified by sample identification number, and the testing sites will have no access to subject data. Refer to the Section VI.A.1 Study Population/Sample Size for the specimen categories for each group.

The specimens obtained prospectively were collected using IRB/IEC approved specimen collection protocols and consent forms that comprehend the testing of these specimens as outlined in this testing protocol. These specimen collection studies were either sponsored by Abbott or by specimen collection vendors. Specimens that are leftover, not individually identifiable were obtained according to the FDA Guidance on Informed Consent for *In Vitro* Diagnostic Device Studies using Leftover Human Specimens that are not Individually Identifiable, April 25, 2006 or specimens were obtained according to applicable laws and guidance regarding informed consent and the use of leftover human specimens. The unidentified specimens are being used when the scientific value is based on characterization of the sample rather than the subject's medical history.

These specimens will be identified by sample identification number, and the testing sites will have no access to subject data. The clinical testing sites will be blinded from knowledge of the specimen categories for specimens provided by Abbott.

Donor specimens may be used to assess system performance. Specimens used for this assessment will be leftover residual samples that have been de-identified and cannot be linked to a subject. These specimens will be re-labeled with a new study identification number (SID).

Confidential Information

This material is the property of Abbott Laboratories and must not be disclosed or used, except as authorized in writing by Abbott Laboratories.

Page 7 of 34

All reports transferred to and communications with Abbott which pertain to specimens in the study must identify each specimen by a sample identification number to ensure subject confidentiality.

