- Subset of preselected *T. cruzi* serology positive and Chagas endemic specimens with limited sample volume that have comparator and supplemental testing data from a previous clinical study. If any discrepant ABBOTT PRISM Chagas results occurs between new results and the previous clinical study results, all of the archived specimens in these 2 categories will be tested with the ABBOTT PRISM Chagas assay.

The Abbott monitor will provide specific details of which specimens do not require comparator testing. All comparator testing will be performed according to the manufacturer's instructions and will include retesting, where required.

The comparator assay results will be compared to the corresponding results of the investigational assay.

E. Supplemental Testing

HIV, HBV and HCV nucleic acid testing (NAT) results for each of the donor specimens will be provided to Abbott to further characterize the donor specimens.

Specimens from donors, individuals at increased risk, individuals from endemic areas, Recovered HBV Individuals (for HBsAg assay) and individuals with HTLV-I/II associated diseases that are repeatedly reactive by either the Alinity s investigational assay or the comparator method or repeatedly gray zone negative (≥ 0.80 S/CO to < 1.00 S/CO) by the Alinity s investigational assay will be further tested using FDA licensed assays or research use only methods. This supplemental testing will be performed at the clinical sites or at external reference laboratories. Results obtained from this testing will be used to better characterize the specimen and assess final status.

The detailed algorithms for supplemental testing will be provided in a separate document for use with the clinical study protocol. Supplemental testing will be performed per each assay algorithm and if a specific assay is no longer commercially available or changes occur in the donor center's routine procedure, a revised version of the algorithm will be provided by the clinical monitor. Additional testing may be performed based on the clinical site's internal supplemental testing procedures. Data generated will be provided to Abbott and will be used for informational purposes.

Preselected positive specimens for each assay will have documented positive results prior to testing at the clinical sites. Supplemental testing is not required, but may be requested by the monitor for troubleshooting purposes.

Confidential Information

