This material is the property of Abbott Laboratories and must not be disclosed or used, except as authorized in writing by Abbott Laboratories.

Page 9 of 34

F. Follow-up Specimens

For all donor specimens with investigational Alinity s results that are discordant with final status after supplemental testing, an attempt will be made to obtain a follow-up whole blood specimen approximately 4 to 6 weeks after initial donation for further analysis. The subject will sign a study specific consent form for collection of the additional specimen. The follow-up specimen will be tested by the applicable investigational Alinity s blood screening assay, the comparator method, and supplemental testing as required.

When a follow-up specimen is not obtained or to obtain additional information when an investigational Alinity s result is discordant with final status, an independent sample from the index donation (e.g., plasma unit) may be tested. Testing on the independent sample may include the investigational Alinity s blood screening assay, the comparator method, and supplemental testing as required.

The follow-up result will be used to better characterize the initial donation and may be used to indicate seroconversion (or rule out seroconversion). If seroconversion occurs and the follow-up results are repeatedly reactive for PRISM and positive on supplemental testing, the status for that donor will be considered positive and the index sample results will be removed from the specificity calculation.

IV. Operating Conditions

A. Material and Equipment

1. Product Description

All investigational products, supplies, and materials will be supplied by Abbott Laboratories.

The investigational products include reagents, calibrators, assay controls, and release controls for each assay, and the consumables and commodities as follows:

Alinity s HIV Ag/Ab Combo	8100/6P01
Alinity s HBsAg	8100/6P02
Alinity s HBsAg Confirmatory	8100/6P03
Alinity s Anti-HCV	8100/6P04
Alinity s Anti-HBc	8100/6P06
Alinity s HTLV-I/II	8100/6P07
Alinity s Chagas	8100/6P08
Alinity s Consumables/Commodities	
* Alinity Trigger	8100/6P11-60
* Alinity Pre-Trigger	8100/6P12-65

Confidential Information

This material is the property of Abbott Laboratories and must not be disclosed or used, except as authorized in writing by Abbott Laboratories.

*	Alinity s Concentrated Wash Buffer	8100/6P13-88
*	Alinity Reaction Vessels	8100/ 6P14-01
*	Alinity s Sample Cups	8100/ 3R01-01

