* Individuals at Increased Risk of HCV Infection	400	X	X
* Preselected Anti-HCV Positive	400	X	X
Alinity s Chagas			
* Individuals from Chagas Endemic Areas	600	X	
* Preselected T cruzi Parasite Positive	100	X	
* Preselected T cruzi Serology Positive	200	X	X

Demographic information including age, gender, and race are documented, where available. Risk factors, medical history, and supplemental results are documented, as applicable.

Confidential Information

This material is the property of Abbott Laboratories and must not be disclosed or used, except as authorized in writing by Abbott Laboratories.

2. Whole Blood Donor and Plasmapheresis Specimens

Plasma or serum specimens from unique blood donors and plasma specimens from unique plasmapheresis donors will be obtained.

Leftover specimens with sufficient residual volume of either plasma or serum specimen will be tested on each Alinity s blood screening assays as shown in the following table.

Assay	Whole Blood Donor (serum or EDTA plasma)*	Plasmapheresis Donor (source plasma)
HIV Ag/Ab Combo HBsAg/Confirmatory Anti-HCV	12,000	3,000
HTLV I/II Anti-HBc Chagas	15,000	NA

*At least one third of total whole blood donors will be EDTA plasma specimens and at least one third will be serum specimens.

No demographic information will be collected from these blood donors.

Inclusion and Exclusion Criteria

Random donor specimens selected for the study must have sufficient volume to complete designated testing. The Abbott monitor will provide the recommended volume requirements for each assay.

The subject/specimen must meet the following inclusion/exclusion criteria to be eligible for participation in this study:

Inclusion Criteria

Serum or EDTA plasma from a whole blood donor for each of the Alinity s assays or a plasmapheresis sample from a plasmapheresis donor (for HIV Ag/Ab Combo, HBsAg & Anti-HCV assays).

Exclusion Criteria

For testing with the Alinity s Chagas assay, exclude donors that have been screened on a previous donation using a licensed test for antibodies to *T cruzi*.

Note: A subject may participate at different times during the study for separate assay studies, but each subject should be represented only once for each assay.

Confidential Information

This material is the property of Abbott Laboratories and must not be disclosed or used, except as authorized in writing by Abbott Laboratories.

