- 2) Refer to the “Specimen Collection and Preparation for Analysis” section of the clinical brochure for detailed procedures on handling of samples prior to placing specimens on the Alinity s System.

Confidential Information

This material is the property of Abbott Laboratories and must not be disclosed or used, except as authorized in writing by Abbott Laboratories.

- 3) A single replicate of each specimen should be tested with the investigational Alinity s assay. Specimens should be placed in barcoded tubes in a sample rack and placed on the Alinity s System to schedule testing.
- 4) Schedule a Alinity s release control for each assay. If release control is not already on the system, place the calibrator and control rack on the Alinity s System in the priority bay to schedule testing.

Note: All testing data generated before the release control will be printed when release control testing is complete.

- 5) Specimens with an initial S/CO result of ≥ 1.00 are considered initially reactive. Specimens with an initial S/CO result ≥ 0.80 to < 1.00 are considered initially gray zone negative. Both initially reactive and initially gray zone negative specimens should be retested in duplicate with the Alinity s method. Specimens with an initial S/CO results of < 0.80 are considered nonreactive and do not require further testing.
- 6) Repeat testing should be performed using the same reagent lot and be done on the same day or the following workday. If greater than 48 hours has elapsed from initial centrifugation, re-centrifuge the sample and document on the Incident CRF. Refer to Alinity s assay clinical brochure for further information regarding centrifugation of specimens.
- 7) If both duplicate retest results are nonreactive ($S/CO < 0.80$), then the specimen is considered negative and no further testing is required. If either retest result has $S/CO \geq 0.80$, then supplemental testing for the assay will be performed.
- 8) Each specimen should be tested with the comparator PRISM method. Specimens initially reactive by the comparator method should be retested in duplicate on the same day or on the next work day of testing. If re-centrifugation is required for the comparator method testing, document on the appropriate CRF. Refer to comparator package insert for further information regarding centrifugation of specimens.
- 9) If the comparator method result is repeatedly reactive, then supplemental testing for the assay will be performed.

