The statistical analysis output along with a listing containing each observation collected for this study will be completed. The listing will be printed for data included in the analysis and excluded from the analysis. The excluded listing will include the reasons for exclusion. A summary of the usage of every test result will also be completed, together with the final analysis results, to ensure that there is no data point missing or misplaced in the analysis.

There is no plan to perform interim analyses that evaluate interim data against acceptance criteria. However, interim data monitoring will be conducted to ensure data meets validity criteria and minimum sample size requirements.

B. Statistical Analysis Description

Confidential Information

This material is the property of Abbott Laboratories and must not be disclosed or used, except as authorized in writing by Abbott Laboratories.

Page 24 of 34

1. Reproducibility

a. Study Design

Assay reproducibility will be determined by testing controls and members of a panel at a minimum of three sites with one instrument using a minimum of 3 lots of each Alinity s blood screening assay reagents, calibrators, and controls.

b. Analysis Variables

The analysis variable is Alinity s assay S/CO values for all panel members and controls.

c. Statistical Analysis Method

The analysis method is based on CLSI EP15-A2E. The reproducibility panel members and the Negative and Positive controls will be tested twice a day for a minimum of 5 days per reagent lot (minimum 3 lots) and site (minimum 3 sites). Within each run, each panel member/control will be tested in two aliquots and two replicates will be assayed per aliquot, resulting in four results per sample.

Overall Analysis

Data from all sites and reagent lots for each reproducibility panel/control member will be used for the reproducibility analysis. The following individual variance components will be estimated: within-run, between-run, between-day, between-lot, between-site, and lot-site interaction. The within-laboratory variance is defined as the summation of within-run, between-run, and between-day variance components. The overall assay variability is defined as the summation of within-run, between-run, between-day, between-lot, between-site, and lot-site interaction variance components. The estimates of the mean S/CO, standard deviation (SD) and %CV will be calculated.

By Site Analysis

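### Does recalling only donors whose Alinity s result disagrees with final status bias the specificity comparison with PRISM enough to need a further analysis?

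*Combined protocol and SAP*

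**What the plan says.** Section III.F (Follow-up Specimens) sets the recall rule: "For all donor specimens with investigational Alinity s results that are discordant with final status after supplemental testing, an attempt will be made" at a second blood draw about 4 to 6 weeks after donation. Section III.B (Ethics) has the same trigger: "if results of the investigational assay do not agree with the final specimen status based on supplemental testing, the donor may be asked" for a follow-up sample. III.F also allows further testing of the index donation when no follow-up specimen is obtained, or "to obtain additional information when an investigational Alinity s result is discordant with final status, an independent sample from the index donation" may be tested.

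If the donor seroconverts and the follow-up is both PRISM repeatedly reactive and supplemental positive, "the status for that donor will be considered positive and the index sample results will be removed from the specificity calculation".

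On the index sample the two assays are treated alike for repeat reactivity. Section III.E sends repeat reactives on either assay to supplemental testing, and step 9 of VI.C.2 says for PRISM: "If the comparator method result is repeatedly reactive, then supplemental testing for the assay will be performed". III.E adds that "HIV, HBV and HCV nucleic acid testing (NAT) results for each of the donor specimens will be provided to Abbott".

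Section IX.B.2.c defines specificity as F/(C + F), the nonreactive share of specimens with negative final status. It gives a second form, F/(C + B + F), that counts reactive indeterminates. Comparator specificity is planned for combined donors and by specimen type. On traceability, IX.A says: "The excluded listing will include the reasons for exclusion. A summary of the usage of every test result will also be completed".

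**The concern.** Section II names a comparison with the licensed assays as part of the objective, so the Alinity s and PRISM specificities will be read side by side. A false-positive result can be reclassified by follow-up for one assay only. If some single-assay reactives are early infections that supplemental testing missed, Alinity s can shed them and PRISM cannot. The plan would then flatter the sponsor's new assay in data meant for regulatory submissions.

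No specificity analysis without the removals is planned. By contrast, reproducibility (IX.B.1.g) is analysed both with and without outliers. It would seem natural to ask for the same treatment here.

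**Working it through.** **1. Trace each reactivity pattern.** Take donors who are supplemental-negative at the index donation.

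| Index pattern | Alinity s agrees with final status? | Recalled? | If infected |
|---|---|---|---|
| Alinity s only | No | Yes | Can be removed: one fewer Alinity s false positive, one fewer PRISM true negative |
| PRISM only | Yes | No | Stays a PRISM false positive and an Alinity s true negative |
| Both | No | Yes | Can be removed: one fewer false positive for each assay |

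Only the first two rows differ between the assays. Removal also needs PRISM reactivity at follow-up, so an Alinity s-only infection that PRISM still misses remains an Alinity s false positive.

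**2. Inputs.** For HIV, HBsAg and anti-HCV, the table in VI.A.2 gives 12,000 whole blood plus 3,000 source plasma donors = 15,000, which matches the stated total. The other three assays have 15,000 whole blood donors. False-positive and seroconverter counts are not given. I assume 15 supplemental-negative repeat reactives per assay, of whom k Alinity s-only donors are removed.

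**3. Effect of removals, all donors.** Alinity s specificity is 1 − (15 − k)/(15,000 − k). PRISM specificity is 1 − 15/(15,000 − k). The gap in percentage points is 100k/(15,000 − k). Intervals are exact (Clopper-Pearson) 95%.

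| k | Alinity s, % (95% CI) | PRISM, % | Gap, points |
|---|---|---|---|
| 0 | 99.9000 (99.8351 to 99.9440) | 99.9000 | 0 |
| 1 | 99.9067 (99.8434 to 99.9490) | 99.9000 | 0.0067 |
| 2 | 99.9133 (99.8518 to 99.9538) | 99.9000 | 0.0133 |
| 3 | 99.9200 (99.8603 to 99.9586) | 99.9000 | 0.0200 |

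The gap formula does not contain the number of false positives, so assuming 5 or 30 per assay gives the same gaps. The interval at k = 0 is 99.9440 − 99.8351 = 0.1089 points wide, about 16 times the effect of one donor (0.1089/0.0067).

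**4. Effect by specimen type.** VI.A.2 says: "At least one third of total whole blood donors will be EDTA plasma specimens and at least one third will be serum specimens". The smallest serum or EDTA group is therefore 15,000/3 = 5,000 or 12,000/3 = 4,000, and source plasma is 3,000. One removal is worth 100/4,999 = 0.020, 100/3,999 = 0.025 and 100/2,999 = 0.033 points. At the same 0.1% reactive rate the exact interval widths are 0.20, 0.23 and 0.27 points.

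**5. Would an analysis without removals help?** Let a be the Alinity s-only and p the PRISM-only early infections, and suppose every a is found. A rule treating both assays alike gives a gap (Alinity s minus PRISM) of about (a − p) × 0.0067.

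- Plan: gap a × 0.0067, error p × 0.0067.
- No removals: gap 0, error (p − a) × 0.0067.

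| a, p | Even-handed gap | Plan's gap (error) | No-removal gap (error) |
|---|---|---|---|
| 2, 0 | +0.0133 | +0.0133 (0) | 0 (−0.0133) |
| 1, 1 | 0 | +0.0067 (+0.0067) | 0 (0) |
| 1, 3 | −0.0133 | +0.0067 (+0.0200) | 0 (+0.0133) |

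With p = 0 the plan is exactly right and the added analysis is wrong. With p greater than a, both err in the same direction, so the even-handed answer lies outside the pair. They bracket it only when p is no larger than a, and p is the quantity that nobody observes.

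**The case for a change.** The best case for acting is that the asymmetry is in the text, its direction favours the sponsor's assay, and an extra table would cost almost nothing. Supplemental testing is even-handed only at the index sample, whereas the imbalance arises at recall. Donor nucleic acid results cover HIV, HBV and HCV, and the documents describe none for HTLV or Chagas. The two specificity formulas differ only over indeterminates, so neither restores a removed donor. The general wording elsewhere (donors may be asked back according to results, and the monitor names those to contact) supplies no PRISM trigger. All of that stands.

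The proposed remedy does not stand. A donor reclassified as positive does not belong in F/(C + F), and restoring that donor counts a confirmed infection as a false positive. The comparison with reproducibility outliers fails because those are measurements of doubtful validity, whereas here the donor's true status has been learned. Counting PRISM-only donors not followed up would cap p, but loosely: with few dual reactives the cap approaches all 15 assumed, or 15 × 0.0067 = 0.10 points, which says little about the likely value.

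It is also too broad to say that everything is reported after removal. III.F confines removal to specificity. The repeat reactive rate, the rate of repeat reactives not confirmed by supplemental testing and the Alinity s-by-PRISM agreement table are not stated to be subject to it. They are a partial substitute only. The two rates are for Alinity s alone, and the plan does not say whether the unconfirmed rate uses index or follow-up status.

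The independent-sample provision adds little. A second sample from the same donation cannot show later seroconversion.

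**Conclusion.** No change to the plan. Follow-up is unequal between the assays and can tilt a descriptive comparison slightly towards Alinity s, but the removal rule agrees with the plan's definition of specificity. An analysis without removals would not repair the unequal follow-up. The gap is 0 to 0.020 points for 0 to 3 one-sided removals among 15,000 donors, and 0.020 to 0.033 points per donor in the smallest specimen-type groups. Each single-donor effect is well inside the corresponding exact interval. No between-assay test, margin or stated decision depends on it.

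These sizes rest on assumed counts. IX.B.2.a treats donors as a presumed zero prevalence population, so the true effect may be nil. The supplemental algorithms are in a separate document, so how often a PRISM-only early infection would be left supplemental-negative cannot be judged here. Any removals can be traced through the planned exclusion listing and agreement table. A report author who sets the two specificities side by side can mention the unequal follow-up without any amendment.

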Specimens should be shipped to Abbott Laboratories for additional testing or to a reference laboratory for supplemental testing as directed by the Abbott monitor. Store the specimens at -20 °C or below and ship overnight on dry ice. When shipped, specimens must be packaged and labeled in compliance with

Confidential Information

This material is the property of Abbott Laboratories and must not be disclosed or used, except as authorized in writing by Abbott Laboratories.

applicable state, federal, and international regulations governing the transport of clinical specimens and infectious substances.

A specimen may be removed from the study if the sample is found unacceptable for testing (e.g. inappropriate handling prior to testing, inadequate volume), or for other assignable causes. The reason for removal must be documented on an Incident CRF. Specimens removed from the study may need to be replaced, if deemed necessary by the Abbott monitor, to meet requirements for the minimum number of specimens.

B. General Study Procedures

1. Assay and/or System Configuration

The investigational Alinity s software is installed onto the Alinity s System at the time of instrument installation. The monitor will provide instructions on software configurations needed to start the study.

2. Instrument System General Procedures

Maintenance procedures are to be performed as instructed in the Investigational Alinity s System Operations Manual. Reports for maintenance and any documentation for component replacements that occurred during the study should be filed in study records.

The on-board inventory of the Alinity s System supplies and reagents will be checked daily. Load consumables and update inventory as necessary.

Refer to the Investigational Alinity s System Operations Manual.

3. Assay Calibration

Each Alinity s blood screening assay will be calibrated as described in the Alinity s Assay Clinical Brochure and the Alinity s Calibrator Clinical Brochure. The calibrator lot number and expiration date information will be read from barcodes when the material is tested on the instrument system. Refer to Calibration Procedures Section of the Alinity s System Operations Manual.

Calibration is to be performed for each investigational reagent lot. Print or transfer electronic report of the calibration and control results for each reagent lot tested. Refer to the Alinity s Assay Clinical Brochure and Alinity s Calibrator Clinical Brochure for frequency of calibration.

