Donor specimens used in the study are collected as part of the routine blood donation process. Events related to the blood or plasma donation process will be handled according to the donor center procedures and not recorded in the study files.

For donor follow-up specimens collected under this protocol, subject adverse events will be documented if they occur. It is expected that drawing blood or plasma may cause pain, bruising, lightheadedness, and on rare occasion, infection

Confidential Information

This material is the property of Abbott Laboratories and must not be disclosed or used, except as authorized in writing by Abbott Laboratories.

Page 23 of 34

at the site of the blood draw. These events will not be recorded as adverse events as they are considered to be normal events that may occur during the course of a blood or plasma draw. Other events that may occur such as fainting, that are not routinely associated with a blood or plasma draw, must be recorded on the Subject Adverse Event Case Report Form and be followed to satisfactory resolution.

A **Subject Adverse Event** is any unfavorable or undesirable medical occurrence (e.g., sign, symptom, or disease) temporally associated with the specimen collection procedure performed.

A **Subject Serious Adverse Event** is an untoward medical occurrence that:

- results in death
- is life-threatening
- requires inpatient hospitalization or prolongation of existing hospitalization
- results in persistent or significant disability/incapacity, or
- results in a congenital anomaly/birth defect.

IX. Statistical Procedures

A. General Information

All data analyses will be performed, and tables and listings of data will be provided by ADD Statistics using SAS version 9.2 or higher.

If revised or additional analyses are required, a description of the additional or revised analyses and justifications for the changes will be documented and approved by the same functional areas as the original approvers to the protocol.

The Abbott monitor will review all test results and may request that certain observations be excluded from analysis if there is an assignable cause, i.e., control or validity criteria failure, instrument errors or problems, acknowledged technologist error, and/or noncompliance with the study protocol. All results tested according to the protocol and not excluded will be eligible for analysis.

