Sensitivity can be also calculated as the proportion of repeatedly reactive (RR) specimens with positive status from specimens with positive status and nonreactive (NR) specimens with indeterminate status:

$$\text{Sensitivity} = A / (A + D + E) \times 100\%$$

A two-sided 95% confidence interval for overall sensitivity will be calculated using the exact method based on the binomial distributions.

All sensitivity calculations described above will also be done for the comparator assay.

d. Sample Size

Sample size for specificity is maximum of 15,000 and calculated based on the minimum power of 80% and $\alpha \leq 0.05$.

Sample size for sensitivity is not determined using statistical power calculations. Sample size is determined by the number of available specimens.

e. Level of Significance/Confidence Statement

Two-sided 95% confidence interval (CI) will be provided.

Confidential Information

This material is the property of Abbott Laboratories and must not be disclosed or used, except as authorized in writing by Abbott Laboratories.

f. Data Handling Convention

All results from this testing that are performed according to the protocol and not excluded will be eligible for analysis. Reasons for any exclusion will be captured in the database.

X. Conduct of the Study

A. Responsibilities for Conduct of the Study

- 1) The investigator will have written and dated approval/favorable opinion from the [Institutional Review Board (IRB) or Independent Ethics Committee (IEC)] for the protocol and other documents as specified by the [IRB/IEC] before initiating the study. In some cases, the [IRB/IEC] may provide an expedited or exception review.
- 2) The investigator is responsible for reporting to the [IRB/IEC] and obtaining the necessary approvals from his/her site administration.
- 3) Abbott Laboratories will not initiate the study until the required pre-study documents are received from the site. Pre-study documents are aligned with GCP requirements and a detailed listing of the required pre-study documents will be provided to the investigator by the Abbott monitor.
- 4) The investigator will perform the study in accordance with GCP. The Abbott monitor will provide the investigator with the GCP-aligned list of investigator requirements.
- 5) The Abbott monitor will provide the investigator with the Guidance for Industry Investigator Responsibilities – Protecting the Rights, Safety, and Welfare of Study Subjects (October 2009) for reference.

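### Can a retest of an independent sample from the index donation change the Alinity s specificity count?

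*Combined protocol and SAP*

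**What the plan says.** Section III.F (Follow-up Specimens) asks for a new blood draw from donors whose Alinity s result disagrees with final status after supplemental testing. It then allows a second material to be used, either because no follow-up draw was obtained or because more information is wanted: "when an investigational Alinity s result is discordant with final status, an independent sample from the index donation (e.g., plasma unit) may be tested". On what may be run, it says "Testing on the independent sample may include the investigational Alinity s blood screening assay, the comparator method, and supplemental testing as required".

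The section gives one rule that alters the count. If the follow-up shows seroconversion, is repeatedly reactive on PRISM and is positive on supplemental testing, "the status for that donor will be considered positive and the index sample results will be removed from the specificity calculation".

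Section IX.B.2.c defines specificity from the Alinity s interpretation and final status, as F/(C + F), where C is repeatedly reactive with negative status and F is nonreactive with negative status. It does not mention the independent sample. Section IX.B.2.f says "All results from this testing that are performed according to the protocol and not excluded will be eligible for analysis". The note in section VI.A.2 says "each subject should be represented only once for each assay".

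Removal is covered in two places. Section VI.A.3 allows a specimen to be removed if unacceptable for testing ("e.g. inappropriate handling prior to testing, inadequate volume), or for other assignable causes"). Section IX.A says "The Abbott monitor will review all test results and may request that certain observations be excluded from analysis if there is an assignable cause", followed by a list of causes.

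**The concern.** The retest is selective. Among donors with negative final status, an Alinity s false positive (cell C) is discordant and qualifies, while a true negative (cell F) is concordant and does not. Any use of the retest to recode or drop a donor would therefore move Alinity s specificity upward or leave it alone. The trigger is Alinity s discordance, so a donor falsely reactive on PRISM alone would not get the same second chance, although comparator specificity is also reported.

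Read literally, the data-handling sentence admits a retest done under III.F as an eligible result, while the VI.A.2 note gives each donor one place per assay. A reactive tube and a nonreactive plasma unit then look like two candidates for that place, with no stated order between them. Section III.E labels sites' own additional supplemental testing with "Data generated will be provided to Abbott and will be used for informational purposes", and III.F has no such label. The removal wording in VI.A.3 is open-ended, and the monitor who may request exclusions sees all the results.

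At stake would be a choice made after results are known, affecting the estimate for which 15,000 donor specimens per assay are collected and which is meant to support regulatory submissions.

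**Working it through.** **Step 1. Which Alinity s result enters the calculation?**

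- Section VI.C.2, steps 3 to 7, defines it: one replicate; a duplicate retest if the signal-to-cutoff ratio is 0.80 or more, with the same reagent lot, on the same or following workday; then an interpretation. Section VI.B.7 adds repeats for error codes or a documented cause.
- Disagreement with final status can be known only after supplemental testing, so a retest triggered by it falls after and outside this sequence.
- The seroconversion rule in III.F takes index results out of the specificity calculation. That makes sense only if index results are what the calculation holds. It is the one exception stated, and a second sample from the same donation cannot show later seroconversion.
- Follow-up draws are also tested on Alinity s. If every such result competed for the donor's single place, follow-up draws would compete too, which is not a sensible reading of IX.B.2.f. Eligible for analysis does not mean counted in specificity.

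**Step 2. Could a nonreactive retest justify exclusion?**

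The causes listed in IX.A are control or validity failure, instrument problems, acknowledged technologist error and protocol noncompliance. A differing result on another sample is none of these. VI.A.3 is looser but requires the reason on an Incident CRF. IX.A also requires a listing of excluded data with reasons, an account of how every test result was used, and justification and approval of any revised analysis by the functions that approved the protocol.

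**Step 3. What would the effect be if the index result did not stand?**

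Inputs: 15,000 donors per assay (III.A, VI.A.2), all taken as status-negative (assumption); specificity F/(C + F) with exact two-sided 95% limits (IX.B.2.c). The documents give no expected false-positive count and no fraction nonreactive on a second sample, so both are assumed.

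| Assumed index false positives | Replaced | Specificity | Exact 95% CI |
|---|---|---|---|
| 15 | 0 | 14,985/15,000 = 99.900% | 99.835 to 99.944 |
| 15 | 5 | 14,990/15,000 = 99.933% | 99.877 to 99.968 |
| 15 | 10 | 14,995/15,000 = 99.967% | 99.922 to 99.989 |
| 5 | 0 | 14,995/15,000 = 99.967% | 99.922 to 99.989 |
| 5 | 2 | 14,997/15,000 = 99.980% | 99.942 to 99.996 |
| 30 | 0 | 14,970/15,000 = 99.800% | 99.715 to 99.865 |
| 30 | 10 | 14,980/15,000 = 99.867% | 99.794 to 99.919 |

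With 15 false positives the interval is 99.9440 − 99.8351 = 0.1089 points wide. Replacing five shifts the estimate by 0.0333 points (0.0333/0.1089 = 31% of the width). Replacing ten shifts it by 0.0667 points (61%), to above the starting upper limit. Removing the donors instead gives almost the same: 14,985/14,995 = 99.933% and 14,985/14,990 = 99.967%. In every scenario, no replacement means no shift.

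The plan's 15,000 cannot be reproduced, because IX.B.2.d gives power and alpha but no null or expected specificity. This check does not depend on it.

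**The case for a change.** The strongest case for a change is that reading intent from context is weaker than a written rule. The independent-sample sentence has no counting instruction, the separate supplemental algorithms are not among the documents supplied, and nothing in the protocol says they decide which Alinity s result is counted. The listing of exclusions gives transparency afterwards, not commitment beforehand. Writing the rule down would need no new testing, draws or consents.

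Much of this stands: no sentence ranks the two results outright, and the one-way selection is real. It does not show that the plan as written leads to a biased estimate. The stated purposes of the extra material are further information or a stand-in for a missing follow-up draw, whose own use is to characterize the donation. Neither purpose is to replace the assay result. For whole blood, VI.A.3 describes the study specimen as residual serum or EDTA tube material, which a plasma unit is not; that argument is weaker for plasmapheresis donors, whose specimen represents the donated plasma.

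A stricter rule could also do harm. Confining results to the steps in VI.C.2 would shut out repeats that VI.B.7 allows. Barring everything from the independent sample could stop its supplemental results from informing final status, although III.F allows that testing.

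**Conclusion.** No change follows. This is a gap in detail that analysts fill sensibly: the index Alinity s result is counted, and only confirmed seroconversion or a documented assignable cause removes it. On that reading the effect on specificity is exactly zero. The shifts of 0.033 and 0.067 points need two things together: a departure from the plan's own sequence and exclusion rules, and assumed figures (15 false positives, with five or ten nonreactive on a second sample) that the documents do not supply. Such specimens have already been repeatedly reactive on duplicate retest, and the documents state no specificity threshold that a shift of this size could cross. The conclusion rests on reading III.F, VI.C.2 and IX.A together, and on the unseen supplemental algorithms not saying otherwise.
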